7.0 REGULATORY AND REPORTING REQUIREMENTS

7.1 Adverse Events (AEs)

Definition: any unfavorable medical occurrence in a human subject including any abnormal sign, symptom, or disease.

This is an observational study where diagnostic imaging and patient reported outcomes are measured in the context of routine breast cancer care. There will be no intervention that is unique to this study that does not normally occur with standard patient care. As such, there are no adverse events that are unique to this study.

Common complications associated with breast oncologic and reconstructive surgery will be tracked since we suspect that complications will be an independent risk for adversely affecting patient reported outcomes independent of tumor: breast ratio. Common complications will be obtained by reviewing the inpatient and outpatient electronic medical records in Clinical Desktop and Allscripts of all enrolled patients. We will therefore record anticipated morbidities such as anesthetic complications, bleeding, infection requiring readmission or surgery, wound healing problems requiring surgical intervention, need for re-excision in lumpectomy due to positive margins, and reconstructive failures due to flap loss or breast prosthesis explant for the purposes of this study. However, none of these are expected to be related to the performance of this study

and will not be summarized, graded or reported as traditional adverse event reporting in an interventional oncology trial.

7.2 Unanticipated Problems

Definition:

- unexpected (in terms of nature, severity, or frequency) given (a) the research procedures that are described in the protocol-related documents, such as the IRB-approved research protocol and informed consent document; and (b) the characteristics of the subject population being studied;
- related or possibly related to participation in the research (“possibly related” means there is a reasonable possibility that the incident, experience, or outcome may have been caused by the procedures involved in the research); and
- suggests that the research places subjects or others at a greater risk of harm (including physical, psychological, economic, or social harm) than was previously known or recognized.

7.3 Noncompliance

Definition: failure to follow any applicable regulation or institutional policies that govern human subject’s research or failure to follow the determinations of the IRB. Noncompliance may occur due to lack of knowledge or due to deliberate choice to ignore regulations, institutional policies, or determinations of the IRB.

7.4 Serious Noncompliance

Definition: noncompliance that materially increases risks, which result in substantial harm to subjects or others, or that materially, compromises the rights or welfare of participants.

7.5 Protocol Exceptions

Definition: A planned deviation from the approved protocol that are under the research team’s control. Exceptions apply only to a single participant or a singular situation.

Pre-approval of all protocol exceptions must be obtained from the Human Research Protection Office prior to the event.

7.6 Reporting to the Human Research Protection Office (HRPO) and the Quality Assurance and Safety Monitoring Committee (QASMC) at Washington University

The PI is required to promptly notify the IRB of the following events:

- Any unanticipated problems involving risks to participants or others which occur at WU, any BJH or SLCH institution, or that impacts participants or the conduct of the study.

- Noncompliance with federal regulations or the requirements or determinations of the IRB.
- Receipt of new information that may impact the willingness of participants to participate or continue participation in the research study.

These events must be reported to the IRB within **10 working days** of the occurrence of the event or notification to the PI of the event.

7.7 Timeframe for Reporting Required Events

Unanticipated Problems	
Any unanticipated events as described in Section 7.2	Immediately, within 24 hours to PI and within 10 working days to the IRB
Noncompliance and Serious Noncompliance	
All noncompliance and serious noncompliance	Immediately, within 24 hours, to PI and within 10 working days to the IRB

7.8 Anticipated Risks

There are no additional risks that this study poses to study participants relative to not participating. All enrolled patients are subject to the same risks as any other patient undergoing standard of care breast oncologic and reconstructive care.

8.0 DATA SUBMISSION SCHEDULE

Case Report Form	Submission Schedule
Original Consent Form	Prior to registration
Eligibility Checklist RedCap Enrollment, Visit 1, Visit 2 MRI, and Visit 3 Plastics (if applicable)	Prior to surgery
RedCap Surgical Intervention	Following receipt of final operative and pathology reports
RedCap Follow-Up Forms Post-Operative Visit 1, Oncology Course, and Post-Operative Visit 2	
Group A:
 
 ○ Post-Lumpectomy 1st post-op visit before Radiotherapy (1-10 weeks after lumpectomy) ○ Post-Lumpectomy post-op visit after radiotherapy (6-18 months after radiation or the latest follow-up time point within the duration confines of our study period.) 
Group B:
 
 ○ Post-mastectomy 1st post-op visit before completion of reconstruction (1-10 weeks after mastectomy) ○ Post-mastectomy Post-op Visit after final reconstruction (3-8 months after final reconstructive procedure or the latest follow-up time point within the duration confines of our study period.) 
Group C:
 
 ○ Post-mastectomy 1st post-op visit (1-10 weeks after mastectomy) Post-mastectomy post-op visit (6-18 months after mastectomy or the latest follow-up time point within the

	duration confines of our study period.)
Unanticipated Event via HRPO	At the time of any unanticipated event
MRI T:B ratio, Breast Q-Scores, and Vectra Mammometrics	The coordinators will ensure MRI performed, Breast-Q's completed and Vectra images captured during active patient phase. MRI T:B ratio will be performed late in the active study phase to allow for a limited number of staff to perform bulk of measurements to optimize standardization. There is also a possibility the software will be upgraded to automate the T:B ratio later in the study period. Breast-Q scores and Vectra mammometrics will be also evaluated in bulk late in the active study phase using SAS, SPSS, or another similar statistical program.

9.0 DATA AND SAFETY MONITORING

In compliance with the Washington University Institutional Data and Safety Monitoring Plan, the Principal Investigator will provide a Data and Safety Monitoring (DSM) report to the Washington University Quality Assurance and Safety Monitoring Committee (QASMC).

The Principal Investigator will review all patient data at least monthly and provide a semi-annual report to the Quality Assurance and Safety Monitoring (QASM) Committee. This report will include:

1. the protocol title, IRB protocol number, and the activation date of the study.
2. the number of patients enrolled to date
3. the date of first and most recent patient enrollment
4. a summary of all unexpected events
5. a response evaluation for evaluable patients
6. a summary of any recent literature that may affect the ethics of the study.

The study principal investigator and Research Patient Coordinator will monitor for unexpected events on an ongoing basis. Once the principal investigator or Research Patient Coordinator becomes aware of a research related and unanticipated adverse event, it will be reported to the HRPO according to institutional guidelines.

10.0 STATISTICAL CONSIDERATIONS

10.1 Outcome Measures

- Tumor: breast ratio generated from MRI
- The Breast Q (pre and post op) outcome measurements
- Breast mammometrics generated from 3D imaging

10.2 Data Fields Recorded

- PATIENT VARIABLES: BMI, smoking history, patient age, race, previous history breast augmentation,
- CANCER VARIABLES: cancer stage, presence or absence of sentinel lymph node biopsy, receptor status, tumor location, multifocal
- RADIATION & CHEMOTHERAPY VARIABLES: radiation received, length of treatment, chemotherapy selected, complications causing radiation or chemotherapy delay or dose reduction
- BREAST VARIABLES: standardized breast measurements (sternal notch to nipple, IMF to nipple, maximum areolar diameter, ptosis)
- SURGICAL VARIABLES: patients undergoing mastectomy with reconstruction as per routine will be recorded as immediate implant, expander-reconstruction, use of acellular dermal matrix, or flap including predominantly DIEP, but also free TRAM, latissimus, PAP, SIEA, TUG, or SGAP. Also balancing procedures will be considered like breast reduction/lift/augmentation/augmentation with lift, fat grafting, adjacent tissue transfer, pseudohernia repair, correction of malposition, implant exchange, capsulectomy, capsulorrhaphy, Ryan procedure,
- IMAGING VARIABLES: tumor: breast ratio, mammometrics (breast volumes, surface area, nipple position, chest wall morphology, vectors, anatomic landmarks)
- COMPLICATION VARIABLES: complications related to breast surgery will be recorded (anesthetic complications, bleeding, infection requiring readmission or surgery, wound healing problems requiring surgical intervention, need for re-excision in lumpectomy due to positive margins, and reconstructive failures due to flap loss or breast prosthesis explant). Patients with complications will be included as this is a key determinant of patient reported outcomes.

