1.0 BACKGROUND AND RATIONALE

1.1 Background

Patients with localized ductal carcinoma in situ (DCIS) and Stage I-IIIA breast cancers are usually candidates for either breast conservation therapy (BCT: lumpectomy with radiation) or mastectomy since survival outcomes are comparable. By its very name, BCT implies superior aesthetic outcomes as breast tissue is preserved. Not surprisingly, when offered, the majority of women will choose BCT over mastectomy with reconstruction, (~65% BCT vs. 35% with mastectomy of which <30% of those receive a reconstruction).

The degree of tissue loss with BCT however falls on a spectrum that is influenced by tumor size and the variable impact of radiation therapy. Large-breasted women are able to absorb a larger absolute tumor resection than smaller breasted women due to the relative size of their breast. Further, the majority of women note that the upper-inner pole of their breast is more aesthetically relevant than other quadrants. Therefore, BCT impacting this region may create a relatively greater degree of dissatisfaction. A recent survey performed by the American Society of Plastic Surgeons found that ~ 46% of women undergoing BCT were disappointed with their results. In another survey – the Breast Cancer Treatment and Outcomes Survey – increased breast asymmetry following BCT was correlated with depressed mood and a feeling of stigmatization. In another study, tumors involving >10% of breast volume, and particularly those located in the medial breast, were associated with decreased patient satisfaction. Unfortunately, quantification of tumor: breast ratio was imprecisely calculated, and patient satisfaction was not determined by a validated, breast-specific patient reported outcomes tool in any of these studies.

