2.2 Secondary Objectives

- Does tumor location impact the influence of tumor: breast ratio on patient reported outcomes following mastectomy with reconstruction or BCT?
- How does the pre and post-op Breast Q for the two groups (mastectomy + recon vs. BCT) reflect the tumor: breast ratio as calculated from 3D images rendered from MRI utilizing software-based algorithms?
- How does the pre and post-op Breast Q for the two groups (mastectomy + recon vs. BCT) reflect the VECTRA 3D generated mammometrics?

- What is the impact of radiation in BCT on Breast Q (Q-score before and after radiotherapy) and VECTRA (breast volume, nipple position, total breast skin surface area before and after radiotherapy)?
- How do complications that arise from each scenario (mastectomy + recon) vs. BCT impact patient satisfaction?
- What is the impact of tumor location and obesity as independent determinants of patient satisfaction in the two groups (mastectomy + recon vs. BCT) relative to tumor: breast ratio?

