Does tumor location impact the influence of tumor: breast ratio on patient reported outcomes following mastectomy with reconstruction or BCT?

- Add location and three way interaction term –group-by-T:B ratio-by-location into Model 2 – (Model 3). The results can be better presented as two graphs – one for each location. See Model 2 for the graph.

How does the pre and post-op Breast Q for the two groups (mastectomy + recon vs. BCT) reflect the tumor: breast ratio as calculated from 3D images rendered from MRI utilizing software-based algorithms?

- Fit and test a model with Q-score as the dependent variable and 3D image data as the independent variable with appropriate non-linear terms for 3D (e.g. spline functions), with group and possible interaction of group-by-3D (Model 4).

How does the pre and post-op Breast Q for the two groups (mastectomy + recon vs. BCT) reflect the VECTRA 3D generated mammometrics?

- Both the Breast Q and the VECTRA 3 D generated mammometrics are continuous variables. The correlation between them will be quantified by Pearson or Spearman correlation coefficient with one sample t test for population correlation coefficient =0, and with Fisher Z transformation to test the population correlation coefficient not equal to zero.

What is the impact of radiation in BCT on Breast Q (Q-score before and after

radiotherapy) and VECTRA (breast volume, nipple position, total breast skin surface area before and after radiotherapy)?

- Perform the subgroup analyses of BCT patients comparing change in outcomes of interest before and after radiation.

How do complications that arise from each scenario (mastectomy + recon) vs. BCT impact patient satisfaction?

- Fit and test a model with Q-score as the dependent variable and complication and group, and possible group-by-complication interaction as independent variables controlling for W in the model.

What is the impact of tumor location and obesity as independent determinants of patient satisfaction in the two groups (mastectomy + recon vs. BCT) relative to tumor: breast ratio?

- Fit and test a model with Q-score as the dependent variable and group, T:B ratio, location, and obesity as the independent variables, controlling for W in the model. Obtain the standardized regression coefficients for location, obesity, and T:B ratio, and compare each other to determine their relative importance.

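### The complication variable covers surgery only, so the secondary objective on complications of each treatment scenario omits radiation complications and undercounts those of BCT

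*Combined protocol and SAP*

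**What the plan says.** Section 1.1 defines the conservation arm's treatment as "BCT: lumpectomy with radiation", and Appendix A labels Group A the BCT plus XRT arm.

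One secondary objective in 2.2 reads "How do complications that arise from each scenario (mastectomy + recon) vs. BCT impact patient satisfaction". It concerns the treatment scenario, not the operation alone.

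The COMPLICATION VARIABLES entry in 10.2 states that "complications related to breast surgery will be recorded". The items in its parenthesis are anesthetic events, bleeding, infection leading to readmission or surgery, wound problems leading to surgery, "need for re-excision in lumpectomy due to positive margins", and reconstructive failure. Section 7.1 has the same scope: "Common complications associated with breast oncologic and reconstructive surgery will be tracked". It introduces its list as examples and names chart review of all enrolled patients as the source.

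A different entry in 10.2, for radiation and chemotherapy, includes "complications causing radiation or chemotherapy delay or dose reduction".

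The model for this objective in 10.5.2 regresses Q-score on "complication and group, and possible group-by-complication interaction as independent variables", controlling for W. It does not define complication or say which field supplies it.

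**The concern.** Radiation is half of what the protocol calls BCT, and section 1.1 itself cites its variable impact on tissue loss. Yet no radiation effect on the breast or chest wall is in the variable that the objective depends on. If the field is used as written, a woman with a radiation complication and no listed surgical event is coded as uncomplicated and joins the reference group.

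At stake is whether the study can answer its own question. As it stands, the model describes surgical complications only, while the objective and any report of it would speak of complications of BCT and of mastectomy with reconstruction. The share of BCT women reported as having a complication would also be too low.

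**Working it through.** **No plan figure to reproduce.** The documents give no complication rate, no radiation-harm rate and no share of Group B irradiated. The only calculated figure, 83 per arm in 10.4, does not bear on this point except as a denominator. What follows shows what can and cannot be derived.

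**1. Scope, side by side.**

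| Element | Covers radiation complications? |
|---|---|
| Objective (2.2) | Yes: complications of each scenario, and BCT includes radiation |
| Complication field (10.2) | No: surgery-related only |
| Tracking rule (7.1) | No: list is illustrative, but of surgical complications |
| Delay/dose-reduction field (10.2) | In part; not linked to the model; misses harms that change neither timing nor dose, including later ones |
| Before/after radiotherapy analysis (10.5.2) | No: average change in BCT patients; does not identify who had a complication |
| W (10.5) | Radiation not named |

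Radiation is not confined to Group A. Section 6.6 allows for it when needed after either operation, and 10.3 expects chemoradiation to vary within each group.

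**2. Undercount in BCT.** Let s be the rate of listed surgical events and r the rate of radiation complications not on that list, assumed independent. The share of BCT women with any complication who are scored as having none is

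r(1 − s) / [s + r(1 − s)].

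| s | r | Calculation | Share missed |
|---|---|---|---|
| 20% | 5% | 0.04 / 0.24 | 17% |
| 20% | 10% | 0.08 / 0.28 | 29% |
| 20% | 20% | 0.16 / 0.36 | 44% |
| 10% | 10% | 0.09 / 0.19 | 47% |
| 30% | 10% | 0.07 / 0.37 | 19% |

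With 83 BCT women, s = 20% and r = 10%, about 83 × 0.08 = 6.6 would be uncounted, against 83 × 0.20 = 16.6 counted. At r = 0 nothing is missed.

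**3. Complication coefficient in BCT.** Take 10 points, the difference that 10.4 treats as meaningful, as the cost of a surgical or a radiation complication alone, and 20 + k as the cost of both. Then

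- mean Q with a surgical event: −10 − 10r − kr
- mean Q without one: −10r
- contrast: −(10 + kr)

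If the second complication costs nothing extra (k = −10), the contrast is −10(1 − r): −9, −8 and −7 at r = 10%, 20% and 30%. If the costs add (k = 0), it is −10 at every r, with no attenuation. If together they cost more than their sum (k > 0), it exceeds 10 in size.

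**4. Interaction.** Suppose all of Group A and a share g of Group B are irradiated, with the same r. The Group A contrast minus the Group B contrast is −kr(1 − g). With k = −10 this is 1, 2 and 3 points at r = 10%, 20% and 30% when g = 0, and 0.5, 1 and 1.5 when g = 50%. With k = 0 it is zero, and with k > 0 it changes sign. If irradiated Group B women have their own rate r_B, the factor becomes r − g·r_B, which can also be negative.

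**5. Reference row.** Whatever k is, the no-complication mean is lowered by 10r in Group A and 10gr in Group B. The gap, −10r(1 − g), is −1, −2 and −3 points when g = 0 and half that when g = 50%. The model would credit it to group, not to complications.

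**6. Timing.** Section 6.5 places Group A's first postoperative Breast-Q before radiotherapy, so radiation harm cannot affect that score. Steps 3 to 5 apply only to the later visit.

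**The case against.** The strongest reply has four parts.

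- **Radiation is not overlooked.** It has its own before/after objective, and 10.2 records both radiation received and complications that delayed or reduced it. Keeping it apart from surgical complications is a legitimate choice. This stands as far as it goes, but neither provision identifies radiation complications for the model, and the objective is not worded as surgical only.
- **The coding is an inference.** Section 10.5.2 never states how complication is scored. That is true. It is still the natural reading, because 10.2 has one field of that name and it is restricted to surgery.
- **One rule governs both arms.** Group B radiation harm short of a listed event is missed too, and re-excision is an item that only lumpectomy patients can incur. This stands. A reader might infer that ascertainment covers all of one arm's treatment and half of the other's, or that the list in 7.1 is closed; the documents support neither.
- **Attenuation depends on a modelling assumption.** This also stands: step 3 shows none when harms are independent and additive. A reader might infer that the analysis would find complications to matter more after reconstruction than after BCT. The documents do not support that direction, since it needs a particular k and a low enough g.

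This is also one secondary objective with only a possible interaction term. Primary Models 1 and 2 do not use the complication variable.

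**Conclusion.** The point holds as a mismatch between objective and exposure. The field in 10.2 leaves out a component of treatment that 1.1 makes part of BCT and that the objective therefore covers. Used as written, it places women whose only complication is from radiation, mainly in Group A but also some in Group B, in the reference group. The analysis then answers a surgical-only question and undercounts BCT complications.

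The undercount follows for any r above zero. Its illustrated size, 17% to 44% of BCT women with a complication at s = 20% and r from 5% to 20%, rests on assumed rates and independence. The size of any distortion in the complication effect, and the direction of any interaction, are undetermined: they depend on radiation-harm rates, additivity and the share of Group B irradiated. The plan should be changed, but the primary analysis is not affected.

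**What to change.** - **Sections 7.1 and 10.2:** add radiation complications of the breast or chest wall as a separate component of COMPLICATION VARIABLES, with a written definition. Ascertain them by the planned chart review in the same way for every irradiated patient in all groups, and do not limit them to events already on the surgical list; a threshold that only re-captures recorded events would add little. Use the radiation part of the delay/dose-reduction field as one source.
- **Section 10.5.2:** state which fields define complication. Fit surgical and radiation components as separate terms, date each complication relative to the Breast-Q visit so that a score is not related to a later event, and report the combined and surgical-only versions alongside.
- **If radiation complications will not be collected:** restate the objective as surgical complications only and add radiation received as a covariate.

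The cost is slightly more abstraction within a review already planned, plus a model term. Records of radiation given elsewhere may be less complete, which should be reported by group.

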10.3 Study Design

All DCIS, LCIS and Stage IA-IIB breast cancers that are reasonably treated with mastectomy or BCT will be screened for eligibility for participation in this study. There will be significant heterogeneity within each group in terms of presence/absence, type, timing (adjuvant/neoadjuvant) and duration of chemoradiation administered. To standardize the timing of our outcome measurement, t=0 will always be in relation to the tumor surgery (lumpectomy or mastectomy). We will also obtain a late time point for last follow-up at least 6 months after the final intervention whether therapeutic or reconstructive, whichever is last. Data collected at this late time point – relative to the initial cancer resection at t=0 – is expected

to vary substantially (months-year) between subjects. We have carefully selected IIB patients as the most advanced stage of breast cancer included. This enables us to evaluate patients with large (>5 cm) tumors that are candidates for mastectomy or BCT which will be important since it is in the larger tumors we hypothesize that patient satisfaction and mammometric data would favor mastectomy + reconstruction over BCT.

Patients that meet the inclusion criteria but who opt for mastectomy without reconstruction are included as a control group to further evaluate the impact of post-mastectomy reconstruction.

